We will develop an app-based intervention, BRITEPath that enhances the capacity of pediatric primary care to effectively manage depressed and suicidal adolescents by referral to embedded MH services. BRITEPath includes three components delivered by MH clinicians, including (1.) an electronic on-boarding procedure tool that supports MH clinicians, Guide2Brite; (2.) the adolescents' safety planning app, BRITE; and (3.) the clinician dashboard, BRITEBoard, to facilitate treatment planning and communication with other primary care providers.

2.2 The aims and hypotheses related to this specific protocol and submission are below for Phase 1b. Aims of the previous phase are in a University of Pittsburgh OSIRIS IRB protocol submission (#PRO18050281) entitled ETUDES Phase 1a-qualitative. Aims of later phases described briefly will be submitted in subsequent protocols.

PROTOCOL TITLE: The Center for Enhancing Treatment & Utilization for Depression and Emergent Suicidality Phase 1b-Study 3-BRITEPath

We will test the feasibility of using BRITEPath in community & pediatric practices using a stepped wedge design. We hypothesize that participants, parents, and clinicians will find the intervention usable and feasible to deploy. We will assess the impact of BRITEPath alone (compared to its impact as part of iCHART in later phases of the ETUDES Center, by obtaining follow-up phone assessments on suicidality, depression, and functional status at 4 and 12 weeks after intake.

Aim 1b (Phase 1b, Feasibility). We will pilot BRITEPath in sites using a stepped wedge design (50 adolescents aged 12-26 yo). Hypothesis 1b: The use of BRITEPath will decrease depressive symptoms, distress, and suicidality (any self-injurious ideation, urges, or behavior) as well as improve overall functioning compared to TAU.

Criterion for success: 75% of adolescents who receive BRITEPath will use it, and 75% of MH clinicians will use Guide2BRITE and BRITEBoard.

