PROTOCOL TITLE: The Center for Enhancing Treatment & Utilization for Depression and Emergent Suicidality Phase 1b-Study 3-BRITEPath

parents and patients. The simplicity and flexibility of BRITEPath would allow for its dissemination to reach beyond specialty MH clinics and is consistent with the NIMH 2015 Strategic Plan emphasizing the need for individualized strategies to improve patient outcomes.

It is impractical for MH clinicians to offer BRITEPath only sometimes and to some patients and not others. Although a cluster randomized trial could address this issue, this design is not feasible for a pilot study. Thus, we will utilize a stepped wedge design in which all practices start with Treatment As Usual (TAU) initially and are randomly chosen to transition to BRITEPath at different times. All clinics will be initially monitored for at least two months during TAU for the main outcomes of fidelity to delivery of the intervention. This will be followed by a staggered adoption of BRITEPath. At each time period, a new clinic will begin implementing the intervention. Block randomization determines the order each clinic begins BRITEPath. Each time period (approximately 3 months), a web-based system will be used to assign the next clinic to begin using BRITEPath.

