17.0 Data Management* and Confidentiality

A stepped wedge design was selected for both ethical considerations and feasibility. A stepped- wedge cluster randomized trial design involves the sequential random rollout of an intervention over multiple time periods following a “baseline” period when no cluster has been exposed. The crossover is typically in one direction, from control to intervention, and continues until all of the clusters receive the intervention with observations taken from every cluster and at each time period. All 3 studies in the ETUDES Center, and specifically, BRITEPath, will utilize this design. Prior to study start, each site will be randomly assigned to switch from.

Treatment As Usual (TAU) to the intervention. In the proposed stepped wedge design, all practices start with TAU (i.e., PCP referral to embedded MH care) and are randomized to transition to implement BRITEPath at different times. All clinics will be initially monitored for at least 2 months during TAU, followed by a staggered adoption of BRITEPath. During each time period, a new clinic will begin to use BRITEPath (order determined by block randomization). A webbased system will randomly assign the next clinic to begin.

With regard to the stated hypothesis: We will perform multilevel modeling to explore time- and intervention-level factors associated with BRITEPath’s use. We will first conduct t-tests for continuous variables and chi-square tests for categorical variables to examine baseline differences in demographic and clinical variables. We will use generalized linear mixed models (nesting for site) to examine between intervention differences in readiness. Distinguishing characteristics will be included as covariates in models examining treatment effects.

Due to the pilot nature of this study, sample size and power considerations center around the precision of confidence interval (CI) width estimation for feasibility outcomes. In this development phase (Aim 1), a sample size of 50 affords us a 95% CI width of no more than 0.28.

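### The 0.28 confidence-interval width is right for 50 independent patients, but is not supported for the adolescent-use criterion, which counts only BRITEPath recipients

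*Combined protocol and SAP*

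**What the plan says.** Section 17.0 explains that, because this is a pilot, sample size is judged by interval width for feasibility outcomes, and states that "a sample size of 50 affords us a 95% CI width of no more than 0.28". It gives no interval method, assumed proportion, intraclass correlation (ICC) or design effect.

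Section 2.0 sets the adolescent success criterion: "75% of adolescents who receive BRITEPath will use it". The denominator is recipients.

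On who the 50 are, the document points two ways.

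- **Some of the 50 are in TAU.** Aim 1b in Section 2.0 says "We will pilot BRITEPath in sites using a stepped wedge design (50 adolescents aged 12-26 yo", and Sections 1.0 and 26.1 give 50 as the study total. Section 6.0 says "all practices start with Treatment As Usual (TAU) initially and are randomly chosen to transition to BRITEPath at different times". Section 17.0 describes a rollout that "continues until all of the clusters receive the intervention with observations taken from every cluster and at each time period", and adds "During each time period, a new clinic will begin to use BRITEPath (order determined by block randomization". Section 15.0 refers to youth in both a TAU and an intervention group. Hypothesis 1b is a comparison with TAU.
- **Every enrolled patient receives BRITEPath.** The study-intervention text in Section 6.0 and the consent text in Section 22.0 go straight from consent to BRITEPath. Section 13.0 places the baseline call after the intervention. Section 12.0 counts about 10 patients per site as having completed both consent and intervention.

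Nowhere is there a TAU/BRITEPath split, a separate TAU number or a number of clinics.

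**The concern.** The interval width is the plan's only sample-size justification, and adolescent use is one of its two success criteria. A reader would naturally take 0.28 as the precision with which adolescent use will be known. That is right only if the denominator is essentially all 50 patients and they behave as independent observations. If part of the 50 is TAU, the stated width is too narrow for this criterion. If none is, the width is nearly right, but the comparison in Hypothesis 1b has no control patients within the stated sample. Either way, the reader cannot tell what the 50 will deliver.

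**Working it through.** **Inputs from the document:** n = 50 and width 0.28 (Section 17.0); 75% among recipients (Section 2.0); about 10 patients per site (Section 12.0); at least 2 months of TAU, then steps of about 3 months (Sections 6.0 and 17.0); enrolment from 8/2019 to 2/2020 (Section 9.0).

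**Inputs assumed:** the number of recipients r and the ICC, neither of which is stated.

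**1. Reproduce the stated figure.** Wald full width = 2 × 1.96 × √(p(1−p)/n). At p = 0.5 and n = 50: 3.92 × √(0.25/50) = 0.277, which rounds to 0.28. At n = 49 it is 0.280 and at n = 48 it is 0.283. As a worst-case bound, 0.28 therefore needs at least 49 independent patients in the denominator.

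**2. Recipients if the 50 includes TAU.** Assume TAU patients do not receive BRITEPath later, and that accrual is even across clinics and periods of a complete wedge. With k clinics, k+1 equal periods and one crossover per period, the BRITEPath cells are k(k+1)/2 out of k(k+1), which is one half for any k. So r = 50 × 0.5 = 25.

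**3. Check that against the calendar.** Section 6.0 says "Each time period (approximately 3 months), a web-based system will be used to assign the next clinic to begin using BRITEPath". With a first crossover at month 2 and steps of 3 months, crossovers fall at months 2, 5, 8 and so on. The 6 to 7 months of enrolment in Section 9.0 would contain at most two. That does not fit a complete wedge with more than two clinics, and it would give fewer recipients than an even split. No single recipient count follows from the document's timing, so 25 is an illustration.

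**4. Width by number of recipients, without clustering.**

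| Recipients r | p = 0.5 | p = 0.75 |
|---|---|---|
| 50 | 0.28 | 0.24 |
| 40 | 0.31 | 0.27 |
| 30 | 0.36 | 0.31 |
| 25 | 0.39 | 0.34 |

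At 75% observed use, the interval is 0.75 ± 1.96 × √(0.1875/25) = 0.58 to 0.92 with 25 recipients, and 0.63 to 0.87 with 50. At 75%, a width of 0.28 needs 37 independent recipients (37 gives 0.279; 36 gives 0.283).

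**5. If all 50 are recipients.** The remaining question is clustering by site. With m = 10 per site, the design effect is 1 + 9 × ICC.

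| Assumed ICC | Design effect | p = 0.5 | p = 0.75 |
|---|---|---|---|
| 0 | 1.00 | 0.28 | 0.24 |
| 0.01 | 1.09 | 0.29 | 0.25 |
| 0.05 | 1.45 | 0.33 | 0.29 |
| 0.10 | 1.90 | 0.38 | 0.33 |

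At p = 0.75 the width reaches 0.28 when the design effect is (0.28/0.240)² = 1.36, so ICC = 0.36/9 = 0.04. The worst-case bound at p = 0.5 has almost no slack: (0.28/0.2772)² = 1.020, so it is passed at an ICC of about 0.002.

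**The case against.** The strongest reply is that nothing is miscalculated. The 0.28 is offered for feasibility outcomes in general and does not name the 75% criterion. That criterion is a plain threshold with no test or confidence limit, so no stated decision changes if the width is 0.34 rather than 0.24. This stands in part: the point is an inconsistency about the denominator, not an arithmetic error. But adolescent use is a headline feasibility outcome, and the plan states no other precision for it.

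It can also be said that fewer than 50 recipients is itself an assumption. Section 11 of the design is silent on this in the sense that no part of the document says whether TAU patients could receive BRITEPath once their clinic crosses over, and Section 6.0 speaks of offering it to all patients after the switch. That stands, and the figures above are conditional on it.

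On clustering, the reply largely succeeds. If all 50 are recipients and use is near 75%, 0.28 survives a modest ICC, and no ICC is given against which to call it wrong. The plan does nest by site elsewhere ("We will use generalized linear mixed models (nesting for site", for readiness), so a sensitivity line would be consistent with it, but that is optional.

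A reader might go further and infer from the rollout timing that about half of the 50, or some other definite number, will be recipients. The document does not support that: the number of clinics is not stated, and the enrolment window does not fit a complete wedge at the stated steps. Nor can a site count be safely taken from the 10 per site in Section 12.0, because that sentence counts patients who have completed the intervention and so belongs to the reading in which everyone receives it.

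**Conclusion.** The concern holds as an internal inconsistency that leaves the stated precision unsupported for one criterion. The 0.28 is a correct unclustered worst case for any feasibility proportion measured on all 50. It is not supported for adolescent use, because the document does not settle how many of the 50 are recipients.

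The size depends on which reading is intended. If the 50 includes TAU patients who never receive BRITEPath and accrual is even over a complete wedge, the width is 0.39 at p = 0.5 and 0.34 at 75% use, against 0.28 and 0.24 for 50 independent recipients. If all 50 are recipients, the loss is small: at 75% use the width stays within 0.28 up to an ICC of about 0.04 with 10 per site. In that case the open question is where the TAU data for Hypothesis 1b come from.

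That the passages conflict is clear. Confidence in the magnitude is only moderate, because the split and the ICC are assumed. A reader might also infer that the trial is too small or needs more patients for this criterion. The document sets no target width for adolescent use, so that does not follow.

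**What to change.** 1. Reconcile Sections 2.0, 6.0, 12.0, 13.0, 15.0, 17.0, 22.0 and 26.1 by stating how many of the 50 are expected in TAU and how many are expected to receive BRITEPath. If TAU patients are within the 50, describe their enrolment, consent and baseline call in Sections 6.0, 13.0 and 22.0. If all 50 are recipients, say where the TAU data for Hypothesis 1b come from, or state that the comparison is not available within the 50.
2. In Section 17.0, keep 0.28 only for proportions measured on all 50 without clustering, and add a sentence for adolescent use. Possible wording: Of the 50 participants, [t] are expected in TAU and [r] to receive BRITEPath; for the proportion of recipients who use it, the 95% CI width (Wald, no clustering) is [a] at p = 0.5 and [b] at p = 0.75. The table by number of recipients above supplies entries for r = 50, 40, 30 and 25.
3. Report the interval beside the observed adolescent-use percentage when it is compared with 75%.

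Optional: one sensitivity line for site clustering over a range of assumed ICCs.

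The cost is a less favourable stated precision if r is below 50, plus edits to three procedural sections if TAU patients are within the 50. Restating the figure needs no extra enrolment. If all 50 are recipients and TAU patients are to be added on top, the study-wide total would change, and that is a separate decision for the sponsor.

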18.0 Provisions to Monitor the Data to Ensure the Safety of Subjects*

Data Safety Monitoring Plan

The study is designed to carefully monitor patient and participant safety and the PI is ultimately responsible for ensuring the safety of participants enrolled. During weekly project meetings, the principal investigator and the project coordinator will meet with all staff associated with the research study to monitor reports of abuse, neglect, suicidality, data entry, safety and maintenance of confidentiality for all active participants, course of adverse events, and ongoing symptoms of suicidality. They will review participant enrollment, instrument completion and data collection and determine if any breaches of confidentiality have occurred, or if participants have disclosed concerns that have warranted referral for further assessment or treatment, or if participants have made any complaints related to the conduct of the study. The PI and Project Coordinator will review the appropriate procedures for further assessment and referral in cases where clinical issues have been identified. In the event of a breach of confidentiality, the principal investigator will inform the involved participant and his/her parents that the breach occurred. The affected participant will be assigned a new ID number. The staff involved will continue to be counseled by the principal investigator and retrained on confidentiality principles. Any breaches of confidentiality will be reported to the IRB by the principal investigator. All serious adverse events (SAEs) will be reported to the WPIC Institutional Review Board according to the regulations set forth by the IRB. As defined by the FDA, an SAE is any adverse experiencing occurring during the study or within 30 days from termination of the patient/participant from the study that results in the following outcomes: death, a life-threatening experience, inpatient hospitalization or prolongation of existing hospitalization, persistent or significant disability/incapacity, results in a congenital anomaly/birth defect, or based upon appropriate medical judgement, may jeopardize the participant's health and may require medical or surgical intervention to prevent one of the other outcomes listed in this definition.

Data Safety Monitoring Board

A DSMB committee will be formed to periodically (semi-annually) review data, management of data and patient safety, reporting procedures and any UAPs and SAEs that emerge from the research. All UAPs and SAEs will be documented and reported to the DSMB & Pitt IRB, once a participant's immediate safety and welfare are addressed.

PROTOCOL TITLE: The Center for Enhancing Treatment & Utilization for Depression and Emergent Suicidality Phase 1b-Study 3-BRITEPath

Board members will include at least 3 qualified MD's and/or PhD's experienced in clinical care and research in adolescent suicidal behavior and uptake of technological interventions to address management and treatment of suicidal and/or depressed adolescents, all of whom have been identified upon funding of the ETUDES Center grant. The DSMB will make final conclusions regarding changes to risk-benefit ratio of the study and final recommendations related to continuing, changing, or terminating the study at each of the semi-annual meetings.

Overall data monitoring will be the responsibility of the PIs. During the course of the study, the PIs will follow the progress of the clinical study and data entry to ensure utmost accuracy of the data and to detect any possible errors at an early timepoint. The study coordinators will generate weekly reports, which will include suicidality and adverse events for each subject for review during weekly project meetings as well as an ongoing CONSORT diagram. The data manager, the CCDC at University of Pittsburgh, will also compile DSMB reports, which will include recruitment data, demographic information, serious adverse events, early termination, and protocol deviations, as well as any other information requested by the DSMB.

19.0 Provisions to Protect the Privacy Interests of Subjects

Study procedures have been designed to protect the privacy and confidentiality of the research participants. Throughout the study all data, including that collected during the recruitment phase, will only be identified by a unique identification (ID) number and participant/subject codes using letters and numbers to protect against invasion of privacy. The data will be blinded correspondingly in all data analyses. Only authorized staff will have access to patient information. All study information containing identifying information will be stored separately from the study data and will be stored in a locked filing cabinet. On the other hand, we notify the patient at the beginning of the study if we detect information that could indicate that a participant's life or health is in danger, we will need to bring his/her parents and/or primary care physician and/or outpatient physical or mental health care provider into the discussion.

20.0 Compensation for Research-Related Injury

n/a

21.0 Economic Burden to Subjects

There are no costs to insurance or otherwise to participants if they choose to volunteer for this study.

22.0 Consent Process

INFORMED CONSENT/ *Subjects who are not yet adults (infants, children, teenagers)*

Trained research/site staff will complete verbal informed consent with participant over the phone and provide a copy of the document via email or mail. Upon obtaining informed consent, the site staff will initiate the BRITEPath intervention. Following the intervention, Pittsburgh/ETUDES Center research staff will follow up and complete research phone calls for which participants will be paid.

PROTOCOL TITLE: The Center for Enhancing Treatment & Utilization for Depression and Emergent Suicidality Phase 1b-Study 3-BRITEPath

During the informed consent discussion, the site staff will speak with the parent to obtain permission to enroll the teen in this study and consent for her or his own participation. The staff will also speak with the adolescent to obtain her or his assent. The assessor will ask the family to take the phone call in a private location to decrease confidentiality breaches and discomfort about talking about sensitive topics.

During the consent process, research/site staff will make it clear that participation is voluntary to both the parent and child participants or adult participant if they are 18 at the time of enrollment. If a minor turns 18 years old during the course of the study an additional consent process will occur via the phone to ensure ongoing willingness to participate that Pittsburgh/ETUDES trained research staff will conduct. During each baseline and follow up phone call, Pittsburgh/ETUDES trained research staff will ascertain if the parent and child are still interested in participating in the study questions prior to collecting or updating data. Both the site staff and Pittsburgh/ETUDES trained research staff will make the family aware that they do not have to immediately make the decision to consent and can take the time to think and discuss participation after they receive all the necessary consent and risk information. The staff may also say that their participation will not influence their care or relationship with care providers. The staff will encourage the family to discuss their participation and provide several minutes for adequate reflection time.

Staff from both Pittsburgh and multi-sites are trained to ascertain if a participant is adequately understanding what is being said during the informed consent discussion and the research questions. Staff will describe the study in wording to reflect appropriate literacy level of a teen and parent. Staff will ask if the family has questions throughout the process and provide responses to questions as they arise.

Non-English Speaking Subjects

n/a

Waiver or Alteration of Consent Process (consent will not be obtained, required information will not be disclosed, or the research involves deception)

The research involves minimal risk. No changes will be made to the adolescents' standard clinical care. The BRITEPath intervention and passive sensors augments their care. Further, questions asked as part of study assessments are consistent with those asked at standard visits to their doctor. Project staff trained in the process of informed consent will obtain informed consent for study participation and document that they certify they gave informed consent.

Due to the nature of research activities, which occur within a variety of sites across Western Pennsylvania, NY, Seattle, WA, and Dallas TX, and other states

PROTOCOL TITLE: The Center for Enhancing Treatment & Utilization for Depression and Emergent Suicidality Phase 1b-Study 3-BRITEPath

in the United States, an investigator cannot practicably be available to participate in the consenting process of each subject. An investigator will be made available to those subjects who wish to speak to them.

Research staff will inquire if a parent is biological or adoptive and it will be documented. Adults without this status must present paperwork to the research staff who will filter it to the respective IRBs and legal counsel for review and verify if an adult is legally able to consent for the child, if there is question over legal status.

